
4.6.4 Rules for Participant Termination

Participants may withdraw from the study at any time. Permission will be sought to continue to collect outcome data for use in the analysis.

5 Statistical Considerations and Data Analytic Plan

The effects of the five individual intervention components will be examined by means of a factorial experiment (see Table 3) involving the following factors: 1) Number of telephone coaching Sessions (12 vs. 24); 2) PCP receives reports (no vs. yes); 3) Text messaging (not provided vs. provided); 4) Meal replacements (recommended vs. not recommended); 5) Buddy Training (not provided vs. provided). Although each of these intervention components has been part of a bundled weight loss intervention previously found to be successful, none of those studies was designed to estimate the impact of any individual component.

We initially chose a factorial experimental design with 16 experimental conditions, and have been conducting this experiment. We recently decided that a complete factorial experiment, obtained by adding 16 more experimental conditions to the design for a total of 32, would have statistical properties that better suit our scientific objectives. Table 3 shows all 32 experimental conditions, indicating which ones we have been running to date (not shaded) and which ones we propose to run (shaded).

Please note that we are not introducing any new experimental treatments; the conditions are merely different permutations of the same five individual components.

The statistical analysis plan for the data remains essentially the same as was originally submitted. The only difference is that in the previous design there was some aliasing of effects that does not occur in the new design.

Table 3 Experimental Conditions in Opt-In Design, with New Conditions Shaded				
Coaching Sessions	Report to PCP	Text Messages	Meal Replace	Buddy Training
12	NO	NO	NO	NO
12	NO	NO	NO	YES
12	NO	NO	YES	NO
12	NO	NO	YES	YES
12	NO	YES	NO	NO
12	NO	YES	NO	YES
12	NO	YES	YES	NO
12	NO	YES	YES	YES
12	YES	NO	NO	NO
12	YES	NO	NO	YES
12	YES	NO	YES	NO
12	YES	NO	YES	YES
12	YES	YES	NO	NO
12	YES	YES	NO	YES
12	YES	YES	YES	NO
12	YES	YES	YES	YES
24	NO	NO	NO	NO
24	NO	NO	NO	YES
24	NO	NO	YES	NO
24	NO	YES	NO	NO

24	NO	YES	NO	YES
24	NO	YES	YES	NO
24	NO	YES	YES	YES
24	YES	NO	NO	NO
24	YES	NO	NO	YES
24	YES	NO	YES	NO
24	YES	NO	YES	YES
24	YES	YES	NO	NO
24	YES	YES	NO	YES
24	YES	YES	YES	NO
24	YES	YES	YES	YES

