All of the estimated main effects and interactions will be based on all 32 experimental conditions. For example, the main effect of Number of Coaching Sessions will be estimated by comparing the mean of Experimental Conditions with 12 coaching calls in Table 3 vs. the mean of Experimental Conditions with 24 coaching calls. Similarly, the main effect of PCP report will be estimated by comparing the mean of Experimental Conditions having PCP progress reports sent vs. the mean of Experimental Conditions not having PCP progress reports sent. Note that in each case, all experimental subjects are included in the estimate. That is why factorial experiments can have small sample size/condition and still have excellent power if the overall sample size is sufficiently large.

Primary Aim 1 is to test for differences in weight by intervention components across the timepoints (baseline, 3- & 6-months), under an intent-to-treat basis, using linear mixed models. For each of the five components, we will determine whether there is a difference in change across time using baseline as the reference cell (i.e., 3-months vs baseline and 6-months vs baseline). From one perspective this is a main effect of each component on the pre-post difference. However, statistically these effects will be modeled as component by time interactions, with the 6-month outcome as the primary endpoint. We will also include two way interactions between components (e.g., Component 1 by Component 2 by time interaction). We note that (a) testing 2-way interactions between intervention components is extremely novel, as traditional RCTs are not capable of looking at these effects, and (b) because we will be using effect (-1,1) coding rather

than dummy (0,1) coding, the power for tests of main effects and interactions are identical for effects of identical size. We expect that testing these effects will be valuable, as we may find, e.g., that two intervention components each have independent main effects, but that when combined they offer no incremental effect. Our plan for dealing with such cases is elaborated below.

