Primary Aim 2 is to make decisions about intervention components and component levels based on the factorial experiment results. We propose to use a modified version of a decision making approach frequently used in engineering (Wu & Hamada, 2000), which emphasizes main effects, using interactions as additional valuable information. This emphasis is consistent with our objective of identifying a set of components and component levels in which each component is making a detectable contribution to the overall effect, and any inactive components have been eliminated. We remind the reader that the mixed model analysis will be performed using effect coding, which will keep any covariances among main effects and interactions to a minimum. This makes it reasonable to start the decision making process by examining main effects, and then to consider interactions carefully in subsequent steps in the process. (Recall that our theoretical model does not predict any substantially-sized higher-order interactions, which is the basis for selection of the highly economical fractional factorial design. This Resolution V design enables examination of all two-way interactions.) The decision making process can be summarized as follows: Step 1: Initial tentative selection of components and component levels, consisting of identification of the components that show a significant main effect on the primary outcome variable, weight. If buddy training, recommended meal replacements, texting, or PCP report have a significant main effect, they will tentatively be selected for inclusion in the intervention. If there is a significant positive main effect of Number of Phone Coaching sessions, this is evidence that the more expensive level (24 sessions) performs better than the less expensive level (12 sessions), so it should be selected; otherwise, the less expensive level should be selected. Step 2: Consideration of interactions and final decision. Next we will examine interactions to look for any indication that we should consider reversing a decision made in Step 1. For example, suppose both Texting and PCP Report have significant main effects, so they were tentatively selected in Step 1. If there is a significant negative interaction between them, this means that the combined effect of Texting and PCP Report is less than the sum of the main effects. Suppose Texting has the larger main effect of the two. In that case we will start from the premise that Texting is selected, and then pose this question: When Texting is selected, *does PCP Report have a large enough incremental effect to justify its selection?* This question can be addressed by examining the simple effect of PCP Report when Texting is at the Yes level. Similar decision making logic will be used to examine all significant interactions that involve any components selected in Step 1 to arrive at the final decisions about selection of components and component levels. Step 3: Identifying the combination of components and levels that produces the largest effect that can be obtained for \$500 or less. If the costs associated with the combination of component and component levels selected in the process described above exceeds the upper limit of \$500, it will be necessary to consider less expensive versions of the intervention. Using as a starting point the set of components and component levels selected in Step 2, we will examine various scenarios in which we remove Yes/No components and change the levels of Either/Or components, and compute the expected outcome based on the regression parameters obtained in the statistical analysis to select the one with the largest expected effect that can be delivered for under \$500.

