5.2 Sample Size and Power

We base power on our primary endpoint: weight change from baseline to the 6-month timepoint. Our interest is in identifying the intervention components that make a more than minimal contribution to average weight loss, or conversely to identify those components that have minimal or no effect on weight loss. Our operational definition of more than minimal is a component effect size of .25 (mean difference divided by standard deviation). Thus, we have powered the study to detect effects of .25 or greater. Using the standard deviation estimate of 4 kg from Amundson et al (2009), which had a follow-up time similar to ours, this translates to a 1 kg difference in weight loss; we view weight loss of less than 1 kg as a minimal effect. There are five components in our 2^{5-1} fractional factorial design. Based on the minimal detectable effect size of .25, the total sample size will be 560 subjects. Based on our previous MBC and PDA+ studies, we conservatively assume an attrition rate of 10% at the 6-month timepoint, so that there will be approximately 504 subjects at this timepoint. Thus, each of the component main effect estimates will be based on 504 subjects, that is, 252 subjects in each of the two levels of the component. Based on these assumptions, we can detect a main effect or interaction effect size of .25 for each component with 80% power under a two-tailed hypothesis test.

Based on our current enrollment as of January 2017, approximately 45% of consented participants were eligible to be randomized after screening. We estimate that we will need to consent approximately 1250 subjects in order to obtain 560 eligible participants for randomization. Of the 560 eligible participants randomized, all will be asked to find a "Buddy" to participate in the study. We are estimating that approximately 850 "Buddies" will need to be verbally consented. (1250 participants + 850 Buddies = 2100 total to be consented).

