6.2.2 Assessment of Intervention Fidelity

Treatment fidelity will be critically important to preserve since participants will be randomized to 16 different conditions. The coach interface will be programmed to reflect the participant's treatment assignment and will prompt the coach to intervene appropriately, using fidelity checklist items that display prescribed and proscribed intervention elements. The treatment for each condition will also be manualized for training purposes, and all coaches will be trained to deliver all intervention conditions. Telephone sessions will be audiotaped and a 15% sample rated for treatment fidelity on a quarterly basis. If fidelity falls below 80%, coaches will be retrained. Fidelity checklists specify: a) good counseling practices (e.g., positive regard, active listening); b) intended session content (e.g., portion size estimation); c) unintended session content (i.e., contamination such as evidence of texting a participant not assigned to text messaging or recommending meal replacement to a participant not assigned to that condition). [name] will train the coaches on the intervention and [name] will serve as primary fidelity evaluator. Training will initially involve role-play as coach and participant. Next coaches will observe the Co-I's and Coordinator performing sessions with volunteers. Finally each coach will perform a live dress rehearsal of telephone delivery of each treatment session and condition. They will continue to rehearse until fidelity ratings show that each coach can be certified as competent to deliver all sessions for all conditions. DVD recordings of the trainings will be made and retained in case there is a need to train new coaches or retrain existing ones. Coaches will meet with [name] weekly as a group for clinical supervision.

7. Study Timetable

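### Pooling participants from the 16-cell and 32-cell phases leaves two-way effects partly aliased with three-way effects unless the two half fractions end equal in size

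*Combined protocol and SAP*

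**What the plan says.** Section 5 describes a design changed while the trial was running: "We initially chose a factorial experimental design with 16 experimental conditions, and have been conducting this experiment". The complete factorial is "obtained by adding 16 more experimental conditions to the design for a total of 32". The analysis plan is said to be otherwise essentially unchanged, the one difference being that "in the previous design there was some aliasing of effects that does not occur in the new design".

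For Primary Aim 1, "All of the estimated main effects and interactions will be based on all 32 experimental conditions", and "all experimental subjects are included in the estimate". The model is a linear mixed model with effect coding. It has component-by-time terms and two-way component interactions by time; three-way terms are not mentioned.

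Section 3.5 specifies permuted blocks stratified by gender. No section gives the number randomised under the 16 cells, the allocation over 32 cells after the change, or a rebalancing rule.

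Three places still describe the half fraction. Primary Aim 2 says the absence of predicted higher-order interactions is a point "which is the basis for selection of the highly economical fractional factorial design", and calls the design Resolution V. Section 5.2 says "There are five components in our 2^{5-1} fractional factorial design". Section 6.2.2 says "participants will be randomized to 16 different conditions".

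**The concern.** A Resolution V half fraction of a 2^5 design has defining relation I = ±ABCDE. Within it, each two-way effect is indistinguishable from the three-way effect of the other three components (AB with CDE), and each main effect from a four-way effect. Participants randomised before the change carry that structure into the pooled data. Adding cells dilutes it, but does not remove it from a model that stops at two-way terms unless the original and the added half fractions end with equal numbers.

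The two-way estimates matter for decisions. Under Primary Aim 2, Step 2 can reverse a component choice on a significant two-way interaction, and Step 3 uses the fitted regression parameters to choose the best package within the $500 limit.

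**Working it through.** **The plan's own figure.** Inputs from Section 5.2: effect 0.25 SD, SD 4 kg (so 1 kg), 80% power, two-tailed, 10% attrition. Alpha is not stated; 0.05 two-sided is assumed.

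- Two-group normal formula: 252 per level, 504 in total; 504 / 0.90 = 560.
- Power at 252 per level: 80.1% (80.0% by noncentral t). The plan's N and power reproduce.
- Standard error of an effect: 4 × √(2/252) = 0.356 kg.

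**Alias coefficient.** Let f be the share of participants randomised under the half fraction, and assume equal cells within each half. In effect coding, AB × CDE = ABCDE, which is +1 in one half fraction and −1 in the other. The coefficient of CDE in the estimate of AB is therefore

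c = (share in original 16 cells) − (share in new 16 cells).

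The sign reverses if the original fraction was I = −ABCDE.

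- Later participants spread equally over 32 cells: c = (1 + f)/2 − (1 − f)/2 = f.
- Later participants sent only to the new cells: c = f − (1 − f) = 2f − 1.

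| f | c, equal over 32 | c, new cells only |
|---|---|---|
| 0.10 | 0.10 | −0.80 |
| 0.25 | 0.25 | −0.50 |
| 0.50 | 0.50 | 0 |
| 0.75 | 0.75 | 0.50 |

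The full alias matrix on the 32 effect-coded cells confirms these values for every two-way/three-way pair. Main effects have the same coefficient with four-way effects. Main and two-way effects stay orthogonal to one another, which is why the stated power is unaffected when higher-order effects are absent.

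**Size of the bias (illustration).** Assume a true two-way effect of zero and a complementary three-way effect of 0.5 kg, half the plan's 1 kg threshold. Bias = c × 0.5 kg; the rejection rate is that of a two-sided 5% z-test shifted by bias / 0.356.

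| c | bias (kg) | bias / SE | false-positive rate |
|---|---|---|---|
| 0.2 | 0.10 | 0.28 | 5.9% |
| 0.5 | 0.25 | 0.70 | 10.8% |
| 0.8 | 0.40 | 1.12 | 20% |

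**Cost of fitting the three-way term.** Variance inflation is 1/(1 − c²). Power for a 0.25 SD two-way effect:

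- c = 0.4: inflation 1/(1 − 0.16) = 1.19, power 73%.
- c = 0.6: inflation 1/(1 − 0.36) = 1.56, power 61%.

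**When balance is reachable.** Each half must end with half the sample, so f must not exceed 0.5, and the share of later participants sent to new cells must be 0.5/(1 − f). At f = 0.2 that is 0.5/0.8 = 62.5%; at f = 0.4 it is 0.5/0.6 = 83%. With f above 0.5, the smallest coefficient attainable at N = 560 is 2f − 1.

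**The case against.** The sentence about aliasing is true of a complete 2^5 design. Once all 32 cells are filled, every effect can be estimated separately, balanced or not. What remains is partial non-orthogonality, which biases an estimate only if a non-zero three-way effect is left out, and Primary Aim 2 says no substantial higher-order interactions are predicted. The illustrated biases are all below the 1 kg that the plan regards as minimal. Any mixture of the two sets of cells improves on the complete aliasing of the half fraction. Selection also starts from main effects, which are entangled only with four-way effects.

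All of this stands, and it limits the practical harm. It does not settle the point: the planned fit has the stated property only under a balance that the plan never promises. The expectation of no higher-order effects was the justification for the half fraction, and the sponsor then left that design for one with better statistical properties.

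Three stronger readings are tempting and are not supported:

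- **That equal cells are the only cure.** Fitting the three-way terms, or contrasting unweighted cell means, removes the bias at any f below 1.
- **That the trial is mis-sized because Section 5.2 names a half fraction.** The calculation depends on 252 per level, which is the same in either design.
- **That a term for enrolment phase would repair the aliasing.** Phase is uncorrelated with the two-way columns, because these sum to zero in both the half fraction and the full design. With the term added, the coefficient under equal later allocation stays at 0.20, 0.50 and 0.80 for f = 0.2, 0.5 and 0.8.

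**Conclusion.** The point holds in a limited form. For the pooled model limited to two-way terms, the claim that aliasing is gone is correct only if the two half fractions end equal. Otherwise each two-way estimate includes c times its complementary three-way effect, with c equal to f or 2f − 1 under the two simplest later allocations.

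The size is unknown because f and the later allocation are not in the documents. The kilogram figures rest on an assumed 0.5 kg three-way effect, equal cells within each half, and attrition unrelated to cell. If three-way effects are zero there is no bias. Sample size and power for main and two-way effects are not in question. The leftover half-fraction wording is an editorial inconsistency with no numerical consequence.

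**What to change.** 1. If enrolment is still open, weight the remaining allocation toward the 16 new cells so that the two half fractions end as equal as possible (560/32 = 17.5 per cell). Set the weight from the actual f: sending everyone to the new cells overshoots when f is below 0.5. Cost: a revised block list.
2. Qualify the statement on aliasing. Report the final cell counts and the realised coefficient c computed from them; f itself is the right figure only under equal later allocation. Cost: wording and one table.
3. Prespecify that, before Step 2 acts on a two-way interaction, it is re-estimated with its complementary three-way term, by time, in the model. Cost: one sensitivity fit, with the loss of power shown above, so it should serve as a check and not as the primary fit.
4. Align the half-fraction wording in Section 5 (Primary Aim 2), Section 5.2 and Section 6.2.2 with the 32-cell design. Cost: editing only.

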4.1.1 Recruitment Process

On-line screeners assess for eligibility criteria (demographics, weight), physical activity preparedness, motivational readiness to change, and scheduling availability. (b).Telephone screening. Potentially eligible candidates will be contacted by telephone. Study staff will explain the research, ask the patient's interest in participating in the study, and proceed with a verbal informed consent process. Staff will screen for exclusion criteria, including checking all medications to see if any are listed on the study Exclusionary Medication list. In order to flag participants who live together, a study exclusion criteria, [web screeners will be cross-checked for duplicate addresses and phone numbers](#). Candidates who remain interested and eligible will be scheduled for an in-person Orientation session. Those who provide informed consent will be invited to attend the baseline assessment where we will screen further for entry and exclusion criteria as well as gather baseline data. Anthropometric data will be gathered. We will administer the PRIME-MD to screen out candidates who meet criteria for bulimia, current substance abuse or dependence (besides nicotine dependence), or report active suicidal ideation. Eligible participants will also be required to obtain physicians approval and find a buddy in order to participate in the study. Once participants have been scheduled to attend Randomization, they will complete a pre-Randomization telephone call with their potential Lifestyle Coach in the Opt-IN study. This call will be used to develop rapport, as well as minimize withdrawal once participants have been randomized.

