4.4 Intervention

A. Behavioral Coaching and Curriculum. Treatment will be delivered as 24 online lessons supplemented by individual telephone coaching. All participants will be given the goal of 7% weight loss via calorie reduction from usual intake and increased physical activity. A login to a website will be provided, where participants will be able to access online interactive lessons. Lessons topics, shown in Appendix, will be based on the DPP and Look AHEAD (e.g., self-monitoring, portion size estimation, fat and calorie content of foods, meal and snack patterning, becoming active, stimulus control). Telephone coaching sessions will last approximately 10-15 minutes. At the beginning of each coaching call, coaches will confirm with the participant that they consented or did not consent for the telephone coaching session to be audio recorded, based on what they indicated on the study consent form. Coaches will discuss that week's lesson materials, recapping the main points. The phone session will also include feedback on self-monitoring and goal attainment (observed from uploaded diet and activity data), problem solving about barriers, and motivational interviewing.

B. Dietary Intervention. During the initial baseline assessment, per DPP, participants will receive both a calorie goal and a fat goal (based on 25% of total daily calories from fat). Those weighing 120 to 174 lb at baseline will be instructed to follow a 1200-kcal/d diet (33 grams fat);

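### On its natural reading the primary 6-month contrast is unadjusted change from baseline; stating a common baseline mean, a covariance structure and gender would add a little precision at no cost

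*Combined protocol and SAP*

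**What the plan says.** The model is described under Primary Aim 1 in section 5 (Statistical Considerations and Data Analytic Plan). The aim is to "test for differences in weight by intervention components across the timepoints (baseline, 3- & 6-months), under an intent-to-treat basis, using linear mixed models". Baseline is the reference time, so the two contrasts are 3 months against baseline and 6 months against baseline. The plan explains that, from one perspective, "this is a main effect of each component on the pre-post difference", and then that "statistically these effects will be modeled as component by time interactions, with the 6-month outcome as the primary endpoint". Two-way interactions between components enter in the same way, crossed with time, under effect coding.

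Section 5.2 is in line with a change contrast: "We base power on our primary endpoint: weight change from baseline to the 6-month timepoint". It uses an SD of 4 kg and a 1 kg effect.

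Section 3.5 stratifies randomization by gender only. Section 5 names no covariate for the primary model, neither baseline weight nor gender. It does not say whether component effects at baseline are estimated or set to zero, and it gives no covariance structure for the three weights.

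**The concern.** With complete data and an unstructured covariance, a mixed model that estimates component effects at baseline gives the same 6-month estimate as a comparison of raw change scores. Any part of 6-month change that baseline weight predicts then stays in the residual. Randomization makes the true baseline means equal across conditions, so a model that uses this fact, or that adjusts for baseline weight, removes that part of the residual.

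There is reason to expect some relation here. Section 4.4 states that "All participants will be given the goal of 7% weight loss", so the kilogram target rises with starting weight, and entry BMI runs from 25 to 40.

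Precision matters because Step 1 of the Aim 2 decision process selects components on significance, and Step 3 uses the fitted coefficients to choose the package under $500. There are 15 such tests: 5 main effects and 10 pairs. The covariance is a second gap, because the standard error of the 6-month contrast depends on it.

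**Working it through.** **1. The plan's own figure.** Inputs from section 5.2: effect 1 kg, SD 4 kg, 252 completers per level, two-sided test. Alpha is not stated; I take 0.05.

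SE = 4 × √(2/252) = 0.356 kg. Power = Φ(1/0.356 − 1.96) = 80.1%. The required number is 252 per level, 504 in total, and 504/0.90 = 560. The stated design reproduces, and it does so for unadjusted change.

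**2. What the two models estimate.** I used one simulated complete data set of 504 with unstructured covariance.

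| Model | Estimate (kg) | SE |
|---|---|---|
| Mixed model, component effect at baseline estimated | −0.903 | 0.336 |
| Raw change score | −0.903 | 0.337 |
| Mixed model, baseline means constrained equal | −0.799 | 0.319 |
| 6-month analysis with baseline covariate | −0.799 | 0.320 |

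The first pair agree, and so do the second pair. Whether the planned contrast is adjusted therefore depends on a detail that the plan leaves unstated.

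**3. Size of the gain.** Let r be the correlation of 6-month change with baseline weight. The residual SD after adjustment is 4 × √(1 − r²). With 252 per level and a 1 kg effect:

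| r (assumed) | Residual SD (kg) | SE (kg) | Power | Completers for 80% |
|---|---|---|---|---|
| 0 | 4.000 | 0.356 | 80.1% | 504 |
| 0.15 | 3.955 | 0.352 | 81.0% | 492 |
| 0.20 | 3.919 | 0.349 | 81.7% | 484 |
| 0.30 | 3.816 | 0.340 | 83.7% | 458 |

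The range for r comes from supposing that kg lost rises with baseline weight at slope s, so that r = s × (baseline SD)/4. With s = 5% and a baseline SD of 12 kg, r = 0.05 × 12/4 = 0.15. With s = 7% and 18 kg, r = 0.07 × 18/4 = 0.315. Both slope and SD are assumptions. If instead the variance of weight is the same at baseline and 6 months, baseline SDs of 10-20 kg give power of 80.5-81.7%.

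A 4,000-run simulation at baseline SD 15 kg and slope 7% gave power of 80.3% for change and 83.6% adjusted; the formula gives 82.9% for the adjusted analysis. Reaching 85% would need r of about 0.35, and 90% about 0.50.

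**4. Why the covariance should be stated.** Suppose, for illustration only, that the model had a random intercept and nothing more. It would take the variance of 6-month change to be the average of the three pairwise-difference variances, (V3 + V6 + V63)/3, where V3 and V6 are the variances of change at 3 and 6 months and V63 is that of their difference. Assume change SDs of 3 and 4 kg and a correlation of 0.85:

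- V63 = 9 + 16 − 2 × 0.85 × 3 × 4 = 4.6.
- The average is (9 + 16 + 4.6)/3 = 9.87, an SD of 3.14 kg instead of 4.
- The 6-month SE is understated by 1 − 3.14/4 = 21%, and the true two-sided error rate is about 12.4%.

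With SDs of 3.5 and 4 kg and correlation 0.50, the understatement is about 6% and the error rate about 6.5%. There is no distortion if all three variances are equal.

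**The case against.** The strongest reply is that the plan may already contain the remedy. The terms it names are component by time and pair by time. Read literally, with no component terms at baseline, that is the constrained model. This stands as a possible reading. The reference-time wording, the plan's own gloss of a pre-post difference and the power calculation on raw change all point the other way, but none settles it. It would go too far to say that the plan fits baseline freely.

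The second reply is that the protocol's tie between baseline weight and kilograms lost is weaker than the 7% goal suggests. Section 4.4 B also has coaches adjust calorie goals towards the same absolute rate of loss, 1-2 lb per week, for everyone. The calorie bands allow heavier people more intake, so they do not by themselves show that heavier people lose more. This stands, and it is why the table includes r = 0.

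Third, a reader might infer that the trial is underpowered or the contrast biased. Neither follows: section 5.2 takes no credit for adjustment, and randomization protects the unadjusted contrast.

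Fourth, a reader might infer from step 4 of the working that the planned tests run at a 10-15% error rate. The documents do not support that. They nowhere propose a random-intercept-only fit, and the figure rests on assumed SDs and correlations. What remains is that the covariance is not specified.

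**Conclusion.** The point holds as a gap in specification with a small, free gain attached. As naturally read, the primary contrast is unadjusted change, with no common-baseline constraint, baseline-weight covariate, gender term or covariance structure stated. For r between 0.15 and 0.30, adjustment cuts the SE by about 1-5% and lifts power for 1 kg from 80% to about 81-84%; at r = 0 it does nothing. These figures rest on an assumed r, the plan's 4 kg SD and alpha of 0.05, and they count nothing for gender. Validity and the stated 80% power are not in question. An unstructured covariance also guards against an understated 6-month SE if the variance of change grows over time, although the plan does not commit to a model that would cause one.

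**What to change.** In the Primary Aim 1 text of section 5, state that the linear mixed model:

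- has time, component-by-time and pair-by-time terms and no component terms at baseline, so that baseline means are equal across conditions;
- uses an unstructured 3x3 covariance for the three weights;
- includes gender, with its interaction with time so that it can act on change.

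Keep the mixed model as the primary analysis. A regression of 6-month weight on baseline weight is equivalent only with complete data. With the 10% attrition assumed in section 5.2, it would drop people who lack a 6-month weight and ignore their 3-month weight, which the mixed model uses under the missing-at-random assumption of section 5.1.

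The cost is a few lines of SAP wording. No new data, visits or participants are needed, and the sample size need not change.
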